Secondary Analyses	
 All plasma GSK2646264 concentration data will be graphically represented, descriptively summarised and listed appropriately. Plasma GSK2646264 concentration time data will be analysed using a Non-compartmental Analysis (NCA), if data permit. Pharmacokinetic data will be presented in graphical and/or tabular form and will be summarized descriptively. Descriptive statistics of both raw and change from baseline, where appropriate will be calculated for erythema, oedema, dyspigmentation (and scaling in existing lesions only) and modified RCLASI. Change from baseline in each clinical activity assessment will be analysed using a repeated measures mixed effects model with subject random effect and treatment and baseline activity score as the fixed effect. IFN mRNA data will be normalised, back transformed and log2 transformed mRNA intensity data in each IFN mRNA signature endpoints will be analysed using a mixed model with subject random effect and treatment and baseline intensity as the fixed effect. Fold changes will be derived from the back-transformed estimate of the difference between adjusted means.
Exploratory Analyses	
 Descriptive statistics of both raw and change from baseline will be calculated for exploratory Pharmacodynamic/Biomarker endpoints. Change from baseline in these endpoints may be analysed using a mixed model with subject random effect and treatment and baseline activity score as the fixed effect. If data permits, endpoints may be analysed using a mixed model with subject random effect and skin type as the fixed effect to study the difference due to skin type.

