9. OTHER STATISTICAL ANALYSES

9.1. Exploratory Pharmacodynamic and Biomarker Analyses

9.1.1. Overview of Planned Exploratory Pharmacodynamic and Biomarker Analyses

The pharmacodynamic analyses will be based on the Safety population, unless otherwise specified.

Table 9 provides an overview of the planned pharmacodynamic and Biomarker analyses, with full details of data displays being presented in [Appendix 8: List of Data Displays](#).

Table 10 Overview of Planned Exploratory Pharmacodynamic and Biomarker Analyses

Endpoint	Untransformed				
	Absolute				
	Summary		Individual		
	T	F	L	F	
Skin Biopsy					
IFN proteins (e.g. MxA, CXCL10) in skin biopsies	Y ^{2,3}	Y ³	Y ²	Y ³	
Immune cell proteins (e.g. CD3, CD20, CD11c, CD123, CD68) in skin biopsies	Y ^{2,3}	Y ³	Y ²	Y ³	
Histopathology score in skin biopsies ^[1]	Y ^{2,3}	Y ³	Y ²	Y ³	
pSYK and SYK protein in skin biopsies	Y ^{2,3}	Y ³	Y ²	Y ³	

NOTES :

- T = Table, F = Figure, L = Listing, Y = Yes display generated.
- Stats Analysis = Represents TFL related to any formal statistical analyses (i.e. modelling) conducted.
- Summary = Represents TFL related to any summaries (descriptive statistics) of the observed raw data.
- Individual = Represents FL related to any displays of individual subject observed raw data.
- [1] component scores; parakeratosis, ballooning/hydropic degeneration, epidermal cell-death, junctional and dermal inflammation will not be statistically analysed.
- [2] Include both absolute and change from baseline
- [3]: By Disease Characteristics (Chronic CLE, Acute CLE, Sub-acute CLE, LET and All).

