11.3.4. Efficacy

RCLASI

- Modified RCLASI Activity score will be derived by adding together patient's score for Erythema, Scaling/Hyperkeratosis (group B only) and Edema/infiltration. If any one of these components are missing, then the modified RCLASI Activity Score will be set to missing.

Modified RCLASI Activity score = Erythema + Scaling/Hyperkeratosis (group B only) + Edema/Infiltration

- Overall Modified RCLASI score will be derived by summing the activity and dyspigmentation score. If any one of these components is missing, then the overall modified RCLASI Score will be set to missing.

- Overall Modified RCLASI Score = Modified RCLASI Activity score + Dyspigmentation

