11.8.13. Non-ICH Listings

Non-ICH : Listings					
No.	Population	IDSL / TST ID / Example Shell	Title	Programming Notes	Deliverable [Priority]
Study Population					
34.	Safety	SAFE_L2	Listing of Type of CLE (Group B-Natural Lesions)	Obtained from medical conditions page in eCRF. Under Disease Diagnosis – 2. Disease characteristics.	
Local tolerability					
35.	Safety	SAFE_L1	Listing of local tolerability (Group B-Natural Lesions)	Include maximal dermal response	SAC
RCLASI					
36.	Safety	PD_L1	Listing of RCLASI and components (Group B-Natural Lesions)	Include change from baseline. Include a footnote to explain the derivation	SAC

Non-ICH : Listings					
No.	Population	IDSL / TST ID / Example Shell	Title	Programming Notes	Deliverable [Priority]
Pharmacokinetic					
37.	PK	PKCI1P	Listing of Plasma GSK2646264 Pharmacokinetic Concentration-Time Data (Group B-Natural Lesions)		SAC
38.	PK	PKPL1P	Listing of Derived Plasma GSK2646264 Pharmacokinetic Parameters (Group B-Natural Lesions)		SAC
Pharmacodynamic					
39.	Safety	PD_L2	Listing of transcriptomic mRNA expression in skin biopsies for selected probesets (Group B-Natural Lesions)	See Section 11.3.5 for list of genes and probe-sets to be listed	SAC
40.	Safety		Raw SAS output from the statistical analysis of change from baseline IFN proteins in skin biopsies (Group B-Natural Lesions)		SAC
41.	Safety		Raw SAS output from the statistical analysis of IFN proteins in skin biopsies by skin type (Group B-Natural Lesions)		SAC
42.	Safety	PD10	Listing of Cell Markers from Immunohistochemistry (Group B-Natural Lesions)	Include change from baseline	SAC
43.	Safety	PD_L3	Listing of Histopathology score and components in skin biopsies (Group B-Natural Lesions)	Include change from baseline. Column for Skin Area (e.g. F, G and H). Each subject has two forms. Thus listing will include both values.	SAC
44.	Safety	PD_L4	Listing of QC criteria from Histological scoring form (Group B-Natural Lesions)	This will include listing of QC Criteria section of the form.	SAC

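### The SAP synopsis lets changes in exploratory biopsy markers be adjusted for a baseline activity score, where each protein marker's own pre-dose value in the lesion is available and more suitable

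*SAP*

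**What the plan says.** The SAP synopsis (Section 1) describes three treatment models in sequence.

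- **Clinical score (RCLASI):** a "repeated measures mixed effects model with subject random effect and treatment and baseline activity score as the fixed effect".
- **IFN mRNA:** analysed "using a mixed model with subject random effect and treatment and baseline intensity as the fixed effect".
- **Exploratory pharmacodynamic and biomarker endpoints:** "Change from baseline in these endpoints may be analysed using a mixed model with subject random effect and treatment and baseline activity score" as fixed effects. The synopsis adds that, if data permit, "endpoints may be analysed using a mixed model with subject random effect and skin type as the fixed effect".

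The one activity score with a derivation is in SAP Section 11.3.4: "Modified RCLASI Activity score = Erythema + Scaling/Hyperkeratosis (group B only) + Edema/Infiltration".

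In the body of the SAP, Section 9.1 and Table 10 list only summaries and individual displays for IFN proteins, immune cell proteins, histopathology and pSYK/SYK. A footnote to Table 10 says of histopathology: "component scores; parakeratosis, ballooning/hydropic degeneration, epidermal cell-death, junctional and dermal inflammation will not be statistically analysed". Appendix 6 covers only the IFN mRNA mixed model.

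Section 11.8.13 nevertheless orders Listing 40, "Raw SAS output from the statistical analysis of change from baseline IFN proteins in skin biopsies", and Listing 41, "Raw SAS output from the statistical analysis of IFN proteins in skin biopsies by skin type".

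**The concern.** When a change score is modelled, the natural covariate is the same quantity measured before treatment in the same lesion. It usually carries most of the predictable variation in the change, and it corrects for chance differences between the active and placebo lesions at the start. A clinical redness, scaling and swelling score is a different measurement. Putting it in the protein model leaves the marker's own starting level unadjusted, except to the extent that the two are correlated.

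The display list adds to the difficulty. A programmer who reaches Listings 40 and 41 has to build a protein analysis from two synopsis sentences, one of which names a doubtful covariate, or else omit two ordered deliverables. Either choice would be made once data exist, in a small trial with about 15 patients planned for Group B. SAP Section 11.3.5 names eight single stains, each reported for epidermis, dermis and both combined, which gives 8 x 3 = 24 marker-by-region results to which the choice could apply.

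**Working it through.** The plan states no figure on this point, so the check is mainly a comparison of sections.

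**Which covariate is meant.**
1. The mRNA sentence adjusts for the marker's own baseline. The RCLASI and exploratory sentences on either side of it both adjust for a baseline activity score. The synopsis therefore distinguishes the two kinds of covariate and gives the protein markers the clinical wording.
2. Section 11.3.4 derives an activity score from clinical components only.
3. Section 11.2.2.1 sets the Group B baseline at Day 1 for RCLASI and at Day -5 to Day -3 for skin biopsies. The two differ in visit as well as in nature.
4. Histopathology is a possible exception. Protocol Section 7.6.1 describes that endpoint as a disease activity score, so there the phrase could mean its own baseline. That reading does not fit IFN proteins, SYK/pSYK or immune cells.

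**Whether the better covariate exists.**
1. Protocol Section 7.6.1 takes pre-dose biopsies from both F and G in Group B.
2. SAP Section 8.3.2 defines the mRNA baseline as the pre-dose value of each treated lesion.
3. SAP Section 2.1 says that nobody was randomised in Group A, so Group B is the only group to be modelled.

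**Possible size.** Let r be the correlation between a marker's own baseline and its change. In this paired design it is the within-subject correlation that matters. Assume that the activity score explains none of that relation. Leaving out the own baseline then multiplies residual variance by 1/(1 - r^2), and interval width by the square root of that.

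| r (assumed) | 1/(1 - r^2) | Square root | Interval |
|---|---|---|---|
| 0 | 1.00 | 1.00 | unchanged |
| -0.5 | 1/0.75 = 1.33 | 1.15 | 15% wider |
| -0.7 | 1/0.51 = 1.96 | 1.40 | 40% wider |

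Neither document gives r. Any correlation between the activity score and the marker's baseline would reduce these figures.

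**Listings against planned analyses.**

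| Endpoint | Models specified in Sections 8-9 | Model-output listings ordered |
|---|---|---|
| IFN proteins | 0 | 2 (Listings 40 and 41) |
| IFN mRNA | 2 (treatment; skin type) | 0, although Table 9 marks one |

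Listing 39, the only mRNA listing, holds individual expression values. The mRNA model results do appear in Tables 5.2 and 5.3 and in Figures 5.2, 5.3, 5.5 and 5.6.

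**The case against.** The strongest reply is that the sentence is optional and out of date. It says the analysis may be done, and protocol Section 9.4.3 is equally conditional. The synopsis also keeps an RCLASI model that SAP Sections 2.1 and 8.1.2 withdraw. It describes mRNA baseline as a fixed effect, where Section 8.3.2 treats it as an additional response. Tables 5.4 and 5.5 and Figures 5.7 to 5.12 are descriptive. On this view Section 9.1 governs and no protein model will be run.

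Much of that stands, and it keeps the point small. It does not remove it. Listings 40 and 41 match the pair of synopsis models, and the Table 10 footnote makes sense only if something other than the histology components might be analysed. The protocol also promised full details of any such analysis in the SAP, and the synopsis sentences are all there is.

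It can also be said that adjustment for own baseline is not the only valid method, since the mRNA model handles baseline differently. That is fair. Both methods, however, use the marker's own lesion baseline. Exchanging one lesion-level covariate for another costs no further degrees of freedom.

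Some stronger readings are tempting, but the documents do not support them:

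- **The treatment estimate is biased by regression to the mean.** F and G are randomised 1:1, so regression to the mean cancels in expectation between active and placebo.
- **The mRNA model results are not delivered.** They are, in the tables and figures listed above; only a model-output listing is missing.
- **The SAP contains no protein model at all.** The synopsis names the response, the random effect and the fixed effects.
- **Both listings come from the questioned model.** Both are confined to IFN proteins, and Listing 41 corresponds to the skin-type model, which has no baseline covariate.

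**Conclusion.** The point holds as a limited one. If the optional treatment model is run as the synopsis words it, IFN proteins, SYK/pSYK and immune cells would be adjusted for the clinical activity score, not for their own pre-dose values. The cost would be lost precision and chance baseline imbalance left uncorrected. The range of about 15% to 40% wider intervals is an illustration that depends on the assumed r and on an activity score unrelated to the marker's baseline; the true figure could be smaller.

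A reader might infer that the sponsor deliberately chose the clinical covariate. The text looks more like wording carried over from the RCLASI sentence, but the documents do not settle this. Nor do they settle whether Listings 40 and 41 are mistitled mRNA output. That would explain both the surplus protein listings and the missing mRNA one, yet the title of Listing 40 speaks of change from baseline while the response in Section 8.3.2 is log2 intensity.

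No primary or secondary result is affected.

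**What to change.** In the SAP synopsis, replace the baseline activity score, for these markers, by the marker's own pre-dose value in that lesion. If the model is to be run, specify it in Section 9.1 and add it to Appendix 6.

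As housekeeping, reconcile Listings 40 and 41 with the analyses actually planned. Either retitle them for the two IFN mRNA models of Section 8.3.2, if that was the intention, or add listings for the mRNA model output and keep the protein listings only if a protein model is specified.

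The cost is a synopsis sentence, a short model specification if needed, and some listing titles. The baseline values are already collected, so no extra biopsies, visits or patients are required.

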2. SUMMARY OF KEY PROTOCOL INFORMATION

2.1. Changes to the Protocol Defined Statistical Analysis Plan

The following changes were made to the originally planned statistical analysis specified in the protocol amendment 3 [(Dated: 14/DEC/2017)]:

- The secondary endpoint for the plasma concentration of GSK2646264 is clarified in the RAP:

Secondary Objectives	Secondary Endpoints

 • To evaluate the plasma concentrations of GSK2646264 in patients with CLE 	
 • PK parameters, including but not limited to AUC, Cmax, tmax, half-life ($t_{1/2}$) if data permits.

Since no subjects were randomised into Group A, no outputs will be generated for this part. Listings will be produced for the enrolled (PV failure) subjects in Group A who were not randomised.

[figure not shown]
In the protocol Section 9.4.2, it states that 'Change from baseline in each clinical activity assessment will be analysed for each lesions type'. Due to the small number of patients in the study, no formal statistical analysis will be conducted for the RCLASI scores. Descriptive summary for raw and change baseline scores will be calculated and presented.

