## **Analysis**

All data will be listed and summarised.

Safety data will be presented in tabular and/or graphical format and summarised descriptively according to GSK's Integrated Data Standards Library (IDSL) standards.

Change from baseline in each clinical activity assessment will be analysed by study part; part A will be summarised descriptively and part B will be analysed using a repeated measures mixed model including visit, treatment and lesion position as fixed effects and subject as a random effect. Estimates of the treatment means and differences will be presented with the associated 95% confidence intervals.

Change from baseline in each IFN mRNA signature endpoints will be analysed by study part; part A will be summarised descriptively and part B will be analysed using a mixed model including treatment and lesion position as fixed effects and subject as a random effect. Estimates of the treatment means and differences will be presented with the associated 95% confidence intervals. If the data is not normally distributed a transformation may be applied to the data.

Full details will be provided in the reporting and analysis plan.

In this sponsor-unblinded bilateral design study, 1 or more unblinded data reviews, using all available data to date, may be carried out by senior managers (not involved in the study conduct) and/or study team members (involved in the study conduct) to aid in portfolio and budget decisions. These administrative reviews will have no impact on the ongoing study. Full details will be provided in the reporting and analysis plan prior to the first administrative review.

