## 4.2. Study Overview Schematic

### Treatment Groups and Duration

In group A subjects will receive both active treatment and placebo-to-match treatment which will be randomly assigned to 2 PV lesions (A+C). The skin site from which the biopsy to quantify concentration of drug in the skin in group A is taken (site D) will be randomised 4:1 to receive either active treatment or placebo.

All subjects in group B will receive both active treatment and placebo to match treatment which will be randomly assigned to the two chosen natural lesions (F+G).

The total duration of the study for group A is anticipated to be approximately 14 weeks, consisting of the following: Screening period (up-to 28 days); photoprovocation and lesion development (3 to 15 days); study treatment period (28 days); follow-up period (28 days) or until resolution of PV lesions (whichever is the latter).

The total duration for group B is anticipated to be approximately 12 weeks, consisting of the following: Screening period (up-to 28 days); biopsies followed by 2-4 day healing period; study treatment period (28 days); follow-up period (28 days).

The duration of study treatment will be 28 days of once-daily cream application to a defined skin lesion area not more than 0.5% body surface area ( $\sim 90\text{cm}^2$ ).

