## 6.1. Treatment Assignment

Subjects will be assigned to treatment in accordance with the randomisation schedule generated by Clinical Statistics, prior to the start of the study, using validated internal software.

Skin areas A-C in group A are horizontally distributed across the back of the patient. The PV lesions will be labelled A, B, C. Study drug and placebo will be randomly assigned to lesions A and C. Lesion B will not be assigned a treatment and will be used for the baseline skin biopsy. A further area of uninvolved skin (area D) will also be treated with study drug or placebo in a ratio of 4:1. Another area of uninvolved skin (area E) will not be treated with either study drug or placebo and will be used solely to take a baseline biopsy.

Lesion/Skin Area	Type	Biopsy timing	Receives Drug/Placebo
A	PV lesion	Day 28	✓
B	PV lesion	Baseline	
C	PV lesion	Day 28	✓
D	Uninvolved Skin	Day 28	✓
E	Uninvolved Skin	Baseline	

**Figure 1 Approximate anatomical representation of UV lesion induction sites (A-C) and uninvolvled skin (D and E) for Group A**

Group A subjects will be assigned to the following regimens:

	Skin Sites A/C/D	Assignment ratio
Sequence 1	A/P/A	4
Sequence 2	A/P/P	1
Sequence 3	P/A/A	4
Sequence 4	P/A/P	1

P=Placebo, A= GSK2646264 1%

The nurse administering the treatments may be aware whether a patient is assigned to sequences 1/4 or sequences 2/3, however they will remain blinded to treatment.

In group B, at the day -5 to day -3 visit, prior to pre-dose biopsies being taken, the two chosen lesions will be labelled F and G based on size (F >G). The two lesions will be randomly assigned placebo or study drug. An area of uninvolvled skin (area H) will not

be treated with either study drug or placebo and will be used solely to take a biopsy at baseline. These lesions can be on any part of the body (all 3 lesions must be in the same anatomical area), but the subject must consent to be biopsied from the area with the lesions.

Lesion/Skin Area	Skin Type	Biopsy timing	Receives Drug/Placebo
F	Natural lesion	Baseline and Day 28	✓
G	Natural lesion	Baseline and Day 28	✓
H	Uninvolved Skin	Baseline	

Group B subjects will be assigned to one of the following regimens:

	Skin Sites F/ G	Assignment ratio
Sequence 1	A/P	1
Sequence 2	P/A	1

P=Placebo, A= GSK2646264 1%

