### **9.4. Key Elements of Analysis Plan**

Data will be summarized and analysed according to the GSK reporting standards, where applicable. Complete details will be documented in the RAP. Any deviations from, or additions to, the original analysis plan described in this protocol will be documented in the RAP.

Final analysis of groups A and B will be reported together after all subjects in groups A (up to 5 subjects) and B (approximately 15 subjects) have completed their follow-up visit.

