#### **9.4.2. Secondary Analyses**

All plasma GSK2646264 concentration data will be graphically represented, descriptively summarised and listed appropriately. Plasma GSK2646264 concentration time data will be analysed using a population pharmacokinetics (PK) model developed previously using data from study 200196 (FTIH of GSK2646264). Population PK parameters (Cmax, AUC(0- $\tau$ ) and terminal phase half life (t1/2) will be reported. Pharmacokinetic data will be presented in graphical and/or tabular form and will be summarized descriptively. All pharmacokinetic data will be stored in the Archives, GlaxoSmithKline Pharmaceuticals, R&D.

Descriptive statistics of both raw and change from baseline, where appropriate, (i.e. n, arithmetic mean, standard deviation, minimum, median and maximum) will be calculated

for erythema, oedema, dyspigmentation (and scaling in existing lesions only) and modified RCLASI and summarized study part. All data will be listed.

Change from baseline in each clinical activity assessment will be analysed for each lesion type using a mixed effects model fitting visit, treatment and lesion location as fixed effects and subject as random. Estimates of the differences between GSK2646264 and placebo will be calculated and appropriate statistical inferences based on these results will be made.

Descriptive statistics of both raw and change from baseline data, where appropriate, (i.e. n, arithmetic mean, standard deviation, minimum, median and maximum) will be calculated for the IFN mRNA endpoints and summarized by lesion type (PV and natural lesions). All data will be listed.

If data permits, formal statistical analyses of the IFN mRNA endpoints may be conducted.

Change from baseline in each IFN mRNA signature endpoints will be analyzed by study part using a mixed model including treatment and lesion number as fixed effects and subject as a random effect. Estimates of the treatment means and differences will be presented with the associated 95% confidence intervals. Distributional assumptions underlying the analyses will be assessed as appropriate. If these assumptions are strongly violated, appropriate transformations will be investigated and if required alternative statistical analyses considered.

Full details will be provided in the RAP.

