8.1.2. Planned Efficacy Statistical Analyses

Due to the small number of patients in the study, no formal statistical analysis will be conducted.

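### SAP synopsis still promises an RCLASI model that SAP 2.1 and 8.1.2 drop, and no planned display summarises the within-patient active-minus-placebo difference in Group B

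*SAP*

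**What the plan says.** The protocol planned a model. Its synopsis says "part B will be analysed using a repeated measures mixed model including visit, treatment and lesion position as fixed effects", with subject as a random effect and with treatment differences shown with 95% intervals. Protocol 9.4.2 adds: "Estimates of the differences between GSK2646264 and placebo will be calculated and appropriate statistical inferences based on these results will be made". Protocol 9.4 allows departures from this: "Any deviations from, or additions to, the original analysis plan described in this protocol will be documented in the RAP".

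The SAP uses that allowance. Section 2.1 states: "Due to the small number of patients in the study, no formal statistical analysis will be conducted for the RCLASI scores", and substitutes a descriptive summary of raw and change scores. Section 8.1.2 repeats: "Due to the small number of patients in the study, no formal statistical analysis will be conducted". The SAP synopsis, under Secondary Analyses, nevertheless says: "Change from baseline in each clinical activity assessment will be analysed using a repeated measures mixed effects model", with treatment and baseline score as fixed effects.

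On the design, Protocol 4.2 says "All subjects in group B will receive both active treatment and placebo to match treatment", randomly assigned to lesions F and G. Protocol 6.1 labels the larger lesion F. SAP 11.2.1 treats efficacy as a skin-site-level measurement.

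**The concern.** There are two separate problems.

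First, the SAP gives opposite instructions for a secondary endpoint. A reader of the synopsis expects a model that the body of the document does not contain.

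Second, the replacement drops the comparison that the design was built to make. Each patient is their own control, and the secondary objective is to determine the drug's effect on the clinical activity score. A table that gives one interval for the active lesions and another for the placebo lesions treats the data as two unrelated groups. It does not show how precisely the treatment effect is estimated, and it does not summarise how consistent that effect is across patients.

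**Working it through.** **Which text governs.** The synopsis has a model; SAP 2.1 and 8.1.2 have none. SAP Table 6 has no model-output columns, model checking in SAP 11.6.1 covers only IFN mRNA, and SAP 11.8.6 and 11.8.7 list descriptive displays only. The synopsis model (treatment, baseline score) also differs from the protocol model (visit, treatment, lesion position), so it matches no other text. The synopsis is the outlier.

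**What the RCLASI displays contain.**
- Table 3.1 (shell PD_T1): n, mean, 95% CI of the mean, SD, median and range, by CLE type, treatment and visit. There is no difference row or column.
- Figure 3.1: individual profiles, with active and placebo in separate panels.
- Figure 3.2: means with error bars.
- Listing 36: individual values by subject, sequence, skin site and treatment, with change from baseline.

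None gives the within-patient difference, its SD or its interval.

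**What can be recovered from Table 3.1.** With complete pairs, the mean difference equals the difference of the two means. Its variance is s_A² + s_P² − 2·r·s_A·s_P, where r is the correlation between a patient's two lesions. The table gives s_A and s_P but not r.

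**Precision of the paired difference.** The plan states no RCLASI precision figure to reproduce. Its only Group B precision figure, 0.02 to 0.30 for 1 safety event in 15, does reproduce (Beta(2,15): 0.016 to 0.302) but does not bear on this point.

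The half-width in SDs of the difference is t(0.975, n−1)/√n:

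| n | Source of n | Half-width |
|---|---|---|
| 15 | planned | 2.145/3.873 = 0.554 |
| 12 | protocol 9.2.1 lower scenario | 0.635 |
| 8 | assumed | 0.836 |
| 5 | assumed | 1.242 |
| 4 | assumed | 1.591 |

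Now put this in SDs of the change score, assuming equal SDs for the two treatments. The half-width is t(0.975, n−1)·√(2(1−r)/n). At n = 15 it is 0.783 for r = 0, 0.554 for r = 0.5 and 0.248 for r = 0.9. Table 3.1 would print 0.554 for each treatment in all three cases.

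**If a reader treats the arms as independent.** The ratio of the correct paired half-width to the unpaired one is t(0.975, n−1)·√(1−r)/t(0.975, 2n−2):

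| n | r = 0 | r = 0.5 | r = 0.8 |
|---|---|---|---|
| 15 | 1.05 | 0.74 | 0.47 |
| 8 | 1.10 | 0.78 | 0.49 |
| 5 | 1.20 | 0.85 | 0.54 |

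**Lesion position.** Let d be a common F-minus-G difference in change. The active-minus-placebo difference is then the effect plus d when active is on F, and the effect minus d when it is on G. The plain mean therefore carries d·(n1−n2)/n: 1/15 = 0.067 of d at an 8:7 split, 1/5 = 0.20 at 3:2, and 0 at equal splits.

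Averaging the two sequence means removes d. The half-width, in within-sequence SDs, is t(0.975, n−2)·0.5·√(1/n1+1/n2): 0.559 at 8:7, 0.643 at 6:6, 0.865 at 4:4 and 1.453 at 3:2.

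**The case against.** The synopsis slip alone is editorial. SAP 2.1 declares the change openly under the right heading, 8.1.2 repeats it, and no programmer could build an RCLASI model from this SAP.

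On the paired summary, the information is not lost. Figure 3.1 marks each subject with a symbol, and the Listing 36 shell carries sequence, site and treatment. With about 15 patients, a reader can match lesions and read off direction by hand. The primary objective is safety, there is no power calculation, and SAP 2.4 makes any active-versus-placebo efficacy comparison optional. A 95% CI carries the same information as a 5% paired test, so adding one partly restores what the sponsor declined. The magnitudes are in SD units, rest partly on assumed sizes and correlations, and the paired-to-unpaired ratio falls on both sides of 1.

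Much of this stands. Direction of agreement can be reconstructed, the position share at 8:7 is small, and the numbers do not show which way arm-wise intervals would mislead in this trial. Three points remain:
- Reconstruction by hand is not a prespecified summary, and it yields no stated precision.
- SAP 2.4 leaves the comparison open but names no method or display.
- Small numbers widen a paired interval without preventing one. Table 3.1 already prints 95% intervals by treatment, and SAP 8.3.2 keeps a mixed model with active-versus-placebo intervals for mRNA in the same group.

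**Conclusion.** Both parts hold. The synopsis contradicts SAP 2.1 and 8.1.2 and should be corrected. The RCLASI displays omit the one summary that uses the within-patient design. The mean difference can be recovered from Table 3.1 if pairs are complete; its interval and the spread of individual differences cannot.

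The paired half-width is 0.55 SDs of the difference at the planned 15 patients, rising to 1.24 at an assumed 5. The comparisons with arm-wise intervals assume equal SDs for the two treatments and the correlations shown. No RCLASI SD or final Group B size is given, so the size in score units is unknown.

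The endpoint is secondary and the primary safety analysis is untouched. This is a change that should be made, mainly because it is cheap and answers a stated objective.

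**What to change.** 1. Reword the RCLASI sentence in the SAP synopsis so that it describes a descriptive summary, in line with 2.1 and 8.1.2.
2. Add a block to Table 3.1, for all CLE types combined, giving the per-patient difference (GSK2646264 lesion minus placebo lesion) in change from baseline at Day 14 and Day 28. Do this at least for the modified RCLASI activity score and the overall modified score. Report n, mean, median, range and 95% CI. The mean per-patient difference is the main estimate, and two scores at two visits make four intervals.
3. Give counts of patients whose active lesion improved more than, the same as, or less than the placebo lesion. Counts suit summed ratings.
4. As support, show the differences by sequence (AF/PG, PF/AG), because F is larger by definition and the protocol model adjusted for position.
5. Label the block exploratory estimation, with no test and no p-value.

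The cost is one sentence and one table block from data already collected and listed. The drawback is that wide intervals may be over-read, which is why the block is limited to two overlapping totals and carries the exploratory label.
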